## 2.6 Poor Outcome of Patients with Relapsed/Refractory DS AML

While the majority of DS AML patients (approx. 85%) have a highly favorable outcome across a range of treatment regimens developed by the COG, Berlin-Frankfurt-Münster (BFM), and Japanese study groups, a lack of response to DS-specific AML therapy is associated with a low probability of long-term survival. Three-year OS was 25.9% among 29 children with relapsed and refractory DS AML. Allogeneic HCT was successful only in 2 of 8 recipients. Similar outcomes were reported by a registry-based study with a 3-year OS of 21% among 21 children with DS AML undergoing HCT. Of note, subsequent relapse (cumulative incidence of relapse, CIR, 62%) rather than treatment-related toxicity (CI TRM 25%) was the predominant cause of treatment failure. These observations support the clinical study of an intensification of treatment compared to current DS AML-specific protocols for the high risk group of DS AML.

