## 2.9

### **Interim Analysis of Patients Treated on the Standard Risk Arm**

According to the study analysis plan, an interim analysis of treatment outcomes for lack of efficacy on the Standard Risk (SR) arm (Arm A) was performed after 50% of the expected number of EFS events had been observed (after 8 of 16 events). Based on a model generated using data of SR patients in the historical control (predecessor study AAML0431) and the amount of follow-up available at the time of data cut off (30 June 2018), 2.4 EFS events were expected in SR patients compared to 8 EFS events observed. The projected 2-year EFS for SR patients on AAML1531 is significantly lower than on AAML0431 (85.6% compared to 93.5%, p 0.0002). As of October 5, 2018, 9 of 109 SR patients on AAML1531 have experienced a relapse at 136 to 327 days after study entry. Four of these relapses occurred on therapy (1 during Intensification I, 3 during Intensification II) and 5 during the first 6 months of follow up after completion of protocol therapy. Of the 9 relapsed SR patients, 8 have died.

These data show lack of sufficient efficacy of AAML1531 protocol therapy for SR patients. Based on this information, post-Induction I treatment on the SR Arm A of AAML1531 was permanently closed.

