## 8.0 CRITERIA FOR REMOVAL FROM PROTOCOL THERAPY AND OFF STUDY CRITERIA

### 8.1 Criteria for Removal from Protocol Therapy

- a) PR, RD, or relapse following Induction II.
- b) Persistent CNS leukemia after 6 doses of IT Ara-C after Induction I.
- c) Grade 3 or greater neuropathy, myelitis and nervous system disorder, and other, including cerebellar toxicity from HD Ara-C (HR group, Arm B only).
- d) Refusal of further protocol therapy by patient/parent/guardian.
- e) Completion of planned therapy.
- f) Physician determines it is in patient's best interest.
- g) Development of a second malignancy.
- h) Repeat eligibility studies (if required) prior to the initiation of protocol therapy are outside the parameters required for eligibility (see [Section 3.2](#)).
- i) Failure to obtain a result for the MRD test at the end of Induction I.

Patients who are off protocol therapy are to be followed until they meet the criteria for Off Study (see below). Follow-up data will be required unless patient is taken off study.

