### 8.2 Off Study Criteria

- a) Death.
- b) Lost to follow-up.
- c) Patient enrollment onto another COG study with tumor therapeutic intent (e.g., at recurrence).
- d) Withdrawal of consent for any further data submission.
- e) Tenth anniversary of the date the patient was enrolled on this study.
- f) For patients enrolled after the implementation of Amendment #4A: Patient is Standard Risk (MRD < 0.05% in the bone marrow) after Induction I.

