## 9.0 STATISTICAL CONSIDERATIONS

### 9.1 Statistical Design

This study is a non-randomized study of children with DS and AML. The primary endpoint of interest will be the event-free survival (EFS) from the end of Induction I to failure to achieve remission at the end of Induction II, relapse, occurrence of a second malignancy or death.

Other outcome measures will include average total number of days per patient spent on protocol therapy, early death rates, overall survival from on study, treatment related mortality, relapse risk, percentage of patients experiencing Grade 3 or higher toxicity, time to count recovery, duration of hospitalization, and infection rates.

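### Off-study rule 8.2(c) permits informative censoring of overall survival after relapse, which would push the OS estimate upward by an amount the documents do not let one fix

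*Combined protocol and SAP*

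**What the plan says.** Section 8.2(c) lists as an off-study criterion "Patient enrollment onto another COG study with tumor therapeutic intent (e.g., at recurrence"). Section 8.1 keeps children in follow-up after they stop protocol therapy, so relapse alone does not end follow-up. It then sets the limit: "Follow-up data will be required unless patient is taken off study".

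Section 9.1 defines the primary endpoint, EFS, as time to "failure to achieve remission at the end of Induction II, relapse, occurrence of a second malignancy or death". Its other outcome measures include "early death rates, overall survival from on study, treatment related mortality, relapse risk". Section 9.3.1 gives an estimation method for EFS and a censoring rule for SR children taken off therapy at the arm's closure. It gives neither for OS.

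On prognosis after relapse, Section 2.6 reports: "Three-year OS was 25.9% among 29 children with relapsed and refractory DS AML". The same section gives 3-year OS of 21% in a transplant registry series. For this trial, Section 2.9 reports: "Of the 9 relapsed SR patients, 8 have died".

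**The concern.** Kaplan-Meier estimation assumes that a censored child has the same future risk as the children still being followed. Rule 8.2(c) breaks that assumption when it operates at recurrence. The child who leaves has just had the event that best predicts death, while those who remain are mostly in remission. Each child censored this way can therefore only raise the OS estimate.

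No other route in the documents clearly recovers these deaths. Expedited reporting (Section 11.3, Table B) covers deaths within 30 days of the last dose. Later deaths are covered only if attributable to the agent and not due to recurrence.

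OS bears on the aim, stated in the Abstract, of improving survival for high-risk children. With 41 HR patients planned and about 11 EFS events expected (Section 9.3.2), a few unrecorded deaths would move the estimate visibly.

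**Working it through.** **Plan figures.** The plan states no OS target, OS sample size or OS power, so there is no OS figure to reproduce. The HR null curve in Section 9.3.2, used below, can be checked against the stated 76%:

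S(730) = 0.75 + 0.25 × exp(−0.0037 × 730) = 0.75 + 0.25 × 0.0671 = 76.7%.

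**Inputs from the documents**
- HR null curve as above. For the 88% alternative, the cure fraction is set to 0.875: 0.875 + 0.125 × 0.0671 = 88.3% at 2 years.
- Proportion dying after relapse: 74% (1 − 25.9%), 79% (1 − 21%) or 89% (8 of 9).

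**Assumptions not in the documents**
- f, the share of relapsed children who join another COG treatment study: 10% to 100%.
- Median time from relapse to death, in those who die: 60 or 120 days.
- Off study 14 days after relapse.
- All EFS events are relapses.
- Time runs from the end of Induction I, as in the null curve, whereas the plan counts "overall survival from on study".

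**Method.** For each scenario, 300,000 children were simulated. Kaplan-Meier 2-year OS was computed with full vital status and again with children censored under 8.2(c). Simulation error is about √(0.8 × 0.2 / 300,000) = 0.07 points. The ranges below span the three death proportions and two median times.

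| f | Upward bias, HR null (points) | Upward bias, 88% EFS (points) |
|---|---|---|
| 10% | 1.2 to 1.5 | 0.6 to 0.8 |
| 25% | 3.1 to 3.7 | 1.7 to 2.0 |
| 50% | 6.3 to 7.8 | 3.3 to 4.1 |
| 100% | 13.7 to 16.8 | 7.0 to 8.4 |

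True 2-year OS in these runs is 80.0 to 84.6% at the null and 89.9 to 92.3% at the alternative. As one example at the null, with 89% dying at a median of 60 days, OS of 79.9% is reported as 83.6% at f = 25%, and 80.0% as 87.7% at f = 50%.

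**Second model.** A separate simulation of 400,000 children at the HR null took 3-year OS, with post-event survival of 25.9% at 3 years. With exponential post-event survival, 84.4% becomes 87.6% (f = 25%) and 91.1% (f = 50%). With a plateau at 25.9% and a median of 180 days to death, 82.9% becomes 86.4% and 90.1%. The biases are +3.2 to +3.5 and +6.7 to +7.2 points, in line with the table.

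**In children.** By 2 years the null implies 41 × (1 − 0.767) = 9.6 EFS events, so f = 25% means about 2.4 children and f = 50% about 4.8.

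**In-trial evidence on f.** Eight of 9 SR relapses had a recorded death, so at most 1 of 9 (11%) could have been censored alive by then. If leaving under 8.2(c) meant that the death went unrecorded, the chance of at most 1 of 9 leaving is 10/512 = 2.0% at f = 50%, and 0.75⁹ + 9 × 0.25 × 0.75⁸ = 0.075 + 0.225 = 30% at f = 25%. The exact 95% interval for 8 of 9 is 51.8% to 99.7%, so the upper limit for the share not recorded as dead is about 48%. At f = 10%, an SR simulation with 89% dying at a median of 60 days moves OS from 87.2% to 88.2%.

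**The case against.** The best counter-argument is that the documents do not show OS being censored in this way. Section 8.1 lifts a reporting duty; it does not define OS censoring. Rule 8.2(c) reaches only other COG studies, and Section 3.1.1 says the COG patient ID follows the patient in later dealings with COG, so linkage is possible. The follow-up form schedule is held outside the protocol. All this stands as far as it goes: vital status may be obtained by another route. But the protocol does not commit to it, and the stated rule, followed literally, produces the bias.

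A reader might infer that OS is censored before most deaths. That needs most relapsed children to enter COG studies. No share is given, and the SR report shows 8 of 9 post-relapse deaths on record. It cannot settle the HR arm, for which there are no post-relapse data.

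A reader might also reach 5 to 11 points from 0.76^(1−f), which gives 81.4% at f = 25% and 87.2% at f = 50%. That takes every event as rapidly fatal and every leaver's death as missed. The simulations give smaller figures, and even those err high, because a death without relapse cannot be hidden by 8.2(c).

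Nor do the documents support a firm claim that Arm B would look better than the 76% 2-year OS of MRD-positive AAML0431 children with no life saved. Section 2.2 promises a general comparison of outcomes, but no OS comparison is specified, and it is not said whether AAML0431 had a similar rule.

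Finally, OS carries no hypothesis test, power or monitoring rule, and the standard error of a 76% estimate in 41 children is √(0.76 × 0.24 / 41) = 6.7 points. That limits the weight of the point. It does not remove a one-sided bias that more patients would not cure.

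**Conclusion.** The concern holds in a limited form. Rule 8.2(c), with no OS censoring rule in Section 9, permits informative censoring of a listed secondary outcome, and its direction is upward. At the HR null the size is about 1 to 1.5 points at 10% entry, 3 to 4 at 25% and 6 to 8 at 50%, roughly halved if 2-year EFS is 88%. These figures rest on an assumed entry share, an assumed 60 to 120 days to death and the treatment of all events as relapses. In the SR arm the 2018 report leaves room for about 1 point; in the HR arm the size is open.

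The primary EFS analysis is unaffected when entry follows recurrence, because relapse has already counted as an event. No design figure changes. The correction should be made because the bias is avoidable at little cost, not because a main conclusion depends on it.

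**What to change.** State in Sections 8.2 and 9.1 that vital status (alive or dead, with date) continues to be collected after a child leaves under 8.2(c), for example by linkage through the COG patient ID. State that enrolment on another COG study is not an OS censoring event. OS would be censored only at the last known alive date, loss to follow-up, withdrawal of consent or the tenth anniversary of enrolment.

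For children already off study under 8.2(c), including SR children enrolled before Amendment 4A, retrieve vital status where consent allows before the final OS analysis. Report how many left by this route in each risk group, so that a reader can judge any remaining effect.

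The cost is a sentence or two in each section and a small linkage task for the HR and SR children concerned, with no new visits or procedures. The OS figure may turn out less favourable.

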## 9.0 STATISTICAL CONSIDERATIONS

### 9.1 Statistical Design

This study is a non-randomized study of children with DS and AML. The primary endpoint of interest will be the event-free survival (EFS) from the end of Induction I to failure to achieve remission at the end of Induction II, relapse, occurrence of a second malignancy or death.

Other outcome measures will include average total number of days per patient spent on protocol therapy, early death rates, overall survival from on study, treatment related mortality, relapse risk, percentage of patients experiencing Grade 3 or higher toxicity, time to count recovery, duration of hospitalization, and infection rates.

### 9.2 Patient Accrual and Expected Duration of Trial

AAML1531 will be compared against a fixed 2-year EFS of 93.5% for SR patients and 76% for HR patients which were observed for comparable patients treated on the prior COG study of DS AML patients (AAML0431). For SR patients, assuming a null EFS of 93.5% at 2 years, there is 95% power to detect an alternative EFS of 87% at 2 years with 1-sided testing at the 10% level of statistical significance if there are 200 SR patients who continue to Induction II. For HR patients, assuming a null EFS of 76% at 2 years, there is 80% power to detect an alternative EFS of 88% at 2 years with 1-sided testing at the 10% level of statistical significance if there are 41 high risk patients who continue to Induction II. The necessary sample size was computed using a binomial test. The final analysis of EFS will occur after a minimum of 2 years after the last patient is enrolled.

\* Replaced with Amendment #6

Up to 3% of patients enrolled are expected to be found ineligible, up to 3% are expected to go off protocol therapy at the end of Induction I, and approximately 83% of patients are expected to be SR. Therefore, enrollment of up to 256 patients will be required to assure that there are 200 SR patients who continue to Induction II and there are 41 HR patients continue to Induction II. Based on an accrual estimate of 60 patients per year, accrual of 256 patients is expected to be completed in approximately 4.3 years.

\* Updated with Amendment #4A

As of October 22, 2018, 26 of the 143 patients enrolled are HR patients who continued to Induction II. Up to 3% of patients enrolled are expected to be found ineligible, up to 3% are expected to go off protocol therapy at the end of Induction I, and approximately 83% of patients are expected to be SR. Therefore, enrollment of up to 256 patients will be required to assure that there are 41 HR patients who continue to Induction II. Based on an accrual estimate of 60 patients per year, accrual of an additional 113 patients is expected to be completed in approximately 2 years.

\* Updated with Amendment #6

As of August 25, 2020, 32 of the 222 patients enrolled are HR patients who continued to Induction II and 5 patients have not been risk classified yet. Assuming 10% of enrolled patients will be HR, enrollment of up to 312 patients will be required to assure that there are 41 HR patients who continue to Induction II. Based on an accrual estimate of 60 patients per year, accrual of an additional 90 patients is expected to be completed in approximately 1.5 years.

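### Section 9.2 says 312 patients will assure 41 high-risk patients, but 312 is only the enrolment at which 41 is the expected count; at the plan's own 10% rate the chance of reaching 41 is about 55–62%.

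*Combined protocol and SAP*

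**What the plan says.** Section 9.2 (Patient Accrual and Expected Duration of Trial) sets the HR comparison at a null 2-year EFS of 76% against an alternative of 88%. It claims 80% power "with 1-sided testing at the 10% level of statistical significance if there are 41 high risk patients who continue to Induction II". The power statement is thus conditional on 41.

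The Amendment #6 update in the same section reports the position on August 25, 2020, when "32 of the 222 patients enrolled are HR patients who continued to Induction II". It also notes, of those already enrolled, that "5 patients have not been risk classified yet". It continues "Assuming 10% of enrolled patients will be HR", and concludes that "enrollment of up to 312 patients will be required to assure that there are 41 HR patients who continue to Induction II". It adds that "accrual of an additional 90 patients is expected to be completed in approximately 1.5 years".

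The Amendment #4A update gives the position on October 22, 2018: "26 of the 143 patients enrolled are HR patients who continued to Induction II". It is used below only as accrual data.

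Section 9.2 gives no probability of reaching 41, and no power for a smaller HR group if enrolment stops at 312.

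**The concern.** To say that a ceiling assures a count implies a high probability of reaching it. A ceiling found by dividing the number still needed by the assumed rate only makes the expected count equal to the target. A binomial count falls below its mean a good part of the time, so such a ceiling is enough only somewhat more often than not.

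HR 2-year EFS is one of the two primary aims in Section 1.1. With Arm A closed, it is the only one for which patients are still being accrued. A reader of Section 9.2 would take 41 HR patients, and the 80% power that depends on them, as secured. If they are not, the section should say how likely 41 is and what happens to power below it.

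**Working it through.** **Inputs (all from Section 9.2).** Enrolled: 222. HR patients who continued to Induction II: 32. Not yet classified: 5, already within the 222. Assumed HR rate: 10% of enrolled. Target: 41. Null and alternative 2-year EFS: 76% and 88%. One-sided level: 10%.

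**1. Reproducing the plan's figure.** HR patients still needed: 41 − 32 = 9. Additional enrolment: 9 / 0.10 = 90. Ceiling: 222 + 90 = 312. Time: 90 / 60 per year = 1.5 years. Both stated figures reproduce exactly. The expected final HR count is 32 + 90 × 0.10 = 41.0, so the ceiling has no margin.

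**2. Chance of reaching 41 at 10%.** With m patients still to be classified and HR rate p, the number of further HR patients is taken as Binomial(m, p), and 9 or more are needed.

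- m = 90 (new enrolments only, as in the plan's arithmetic): P(≥ 9) = 55.1%.
- m = 95 (the 5 unclassified patients also count as chances): P(≥ 9) = 61.8%.

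The second matches the stated facts better, because those 5 can still prove to be HR. The first follows the plan's own division.

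**3. Sensitivity to the HR rate (m = 95).**

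| HR rate | Source | P(≥ 41 HR) |
|---|---|---|
| 7.6% | 6 / 79 | 29.5% |
| 8.1% | 6 / 74 | 36.4% |
| 10% | Amendment #6 assumption | 61.8% |
| 14.4% | 32 / 222, cumulative | 94.2% |

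The 6 is 32 − 26 and the 79 is 222 − 143. The 74 removes the 5 unclassified patients, on the assumption that all of them enrolled after October 2018. Both low rates rest on 6 HR patients and on taking the 143 as fully classified in October 2018. They are illustrations, not figures stated in the protocol.

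**4. Size of a shortfall at 10%.** Reaching at least 38 HR patients needs 6 or more further ones. P(≥ 6) = 89.7% for m = 90 and 92.2% for m = 95.

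**5. Effect on power.** Power at n = 41 is compared with power averaged over the distribution of the final HR count, capped at 41, at a 10% HR rate.

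- Log-minus-log test of Section 9.3.1, applied to complete 2-year data without censoring: 78.4% at n = 41; average 76.0% (m = 90) or 76.4% (m = 95). Loss: about 2 points.
- Normal approximation to the binomial test: 75.2% at n = 41; average 74.1% (m = 90) or 74.3% (m = 95). Loss: about 1 point.

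**The case against.** The strongest reply is that this is one overstated verb. If 41 is missed, the miss is probably by a few patients, the average cost is 1–2 points of power, and no endpoint, test or enrolment number changes. The plan already reads as an HR target of 41 with 312 as the cap, and Amendment #6 itself shows the sponsor revising the ceiling when HR accrual lagged. The 10% is also below the cumulative 14.4%, at which 312 would very probably be enough. All of this stands, and it limits the weight of the point. It does not make the sentence correct: no calculation at the plan's own 10% comes near assurance.

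Three stronger readings may occur to a reader, and the documents do not support them.

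- *That Amendment #6 wrongly left out the allowances for ineligibility and for leaving therapy after Induction I.* The earlier calculation applied 3% and 3% and then a risk split. Amendment #6 instead uses a rate per enrolled patient, next to a count of patients who continued to Induction II. Such a rate may already include those losses, and deducting them again could count them twice.
- *That the HR rate has fallen to 8%.* Section 2.9 reports 109 standard-risk patients on October 5, 2018. With the 26 HR patients counted on October 22, that makes 135 of 143, so about 8 may have been pending, ineligible or off therapy. The denominator for the later period is uncertain, and the numerator is 6.
- *That missing 41 by one or two causes a sharp loss of power.* Under the log-minus-log test, power is 78.4% at n = 41, 80.2% at 40 and 67.6% at 39, while the type I error is 10.7%, 12.3% and 6.7%. These jumps come from the discreteness of the test. Likewise, the gap between the stated 80% and 78.4% exists at exactly 41 and has nothing to do with the ceiling.

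**Conclusion.** The claim that 312 assures 41 HR patients is wrong as written. The ceiling is an expected-value figure. On the plan's own 10% it reaches 41 with probability of about 62% counting the 5 unclassified patients, or 55% on the 90 new patients alone. Over a plausible range of HR rates the probability runs from about 30–36% near 8% to about 94% at 14.4%.

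The consequence is modest: at 10%, about a 90–92% chance of at least 38 HR patients and a loss of about 1–2 points of average power. The documents do not support saying that the HR comparison is seriously underpowered or that enrolment must rise. The probabilities assume independent patients with a constant HR rate; the power figures also assume complete 2-year follow-up. The correction is worth making because it concerns the remaining accrual for a primary aim and costs almost nothing.

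**What to change.** Reword the Amendment #6 paragraph of Section 9.2 in three respects.

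1. Replace the claim of assurance with a statement that enrolment of up to 312 *is expected to yield* 41 HR patients who continue to Induction II.
2. State the probability of reaching 41: about 55–62% at a 10% HR rate (the lower figure on the 90 new patients, the higher including the 5 unclassified). Give its range over plausible HR rates, for example about 30–36% near 8% and about 94% at 14.4%, with the low rate labelled as an estimate from 6 HR patients.
3. State that the 80% power applies only if 41 HR patients are reached, and that power for the HR number actually accrued will be reported.

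No extra patients, accrual time or change of analysis is involved. The cost is one paragraph and a slightly less favourable stated figure.
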